9.5 Outcomes

The Primary Outcome and Secondary Outcomes as stated in this section (Sections 9.5.1 and 9.5.2) will be analyzed as specified in the Data Analyses section below (please see below, Section 9.6). The Primary and Secondary Outcomes will be determined based upon the data analyses as specified below in Section 9.6 which will be performed by the study statistician ([name]).

9.5.1 Primary Outcome

The primary outcome is putamen node strength assessed by MRI comparing the value before randomization to the one 12 weeks after randomization.

9.5.2 Secondary Outcomes

The secondary outcomes include the following:

Emotional Problems. Emotional problems will be assessed by the SDQ questionnaire comparing the value before randomization (Visit 1) to the one 12 weeks

after randomization (Visit 14).

Other outcomes

Adherence. The proportion of volunteer randomized to TARA training who participate in at least 75% of the sessions. We expect that at least 80% of participants on the TARA arm will attain this level of adherence.

Safety and tolerability of the intervention. Adverse events will be collected at each visit and graded, and their attribution to their participation will be assessed. The safety of the TARA intervention will be demonstrated if < 15% of the participants experience a grade 2 (moderate) or grade 3 (severe) adverse event related to the TARA intervention.

To demonstrate the tolerability of the intervention used in this study, we will use the Child Session Rating Scale (CSRS) score. The CSRS is a 4-item self-assessments using a 10-cm visual analog scale (Campbell & Hemsley, 2011), with higher scores indicating better experience. This measure of tolerability will be completed after each session. Participants will rate the session in terms of how much they felt listened to, how important the content and activities were to them, how much they liked the session, and their overall experience. The intervention will be tolerable if the median CSRR is at least 20 in >80% of participants.

Retention. To demonstrate the ability to retain subjects, we will retain at least 80% of randomized participants for primary outcome measurement at the end of the study regardless of adherence to the intervention.

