7.1 Specification of Safety Parameters

To demonstrate the safety of the TARA intervention, we will carefully record all adverse events and require that < 15% of the participants experience a grade 2 (moderate) or grade 3 (severe) adverse event related to the TARA intervention.

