9. STATISTICAL CONSIDERATIONS

9.1 General Design Issues

This is a randomized open-label waiting list controlled study of TARA training in 100 boys and girls aged 14-18 years. They will be individually randomized to 12 weeks of group TARA training sessions (50 to TARA training and 50 to waitlist control). The randomization is open label because there was concern that it was not possible to develop a sham training which would motivate participation and yet have no effects on the desired outcomes.

This study is designed to demonstrate that the TARA training will increase putamen connectivity (primary outcome) and decrease emotional problems on the SDQ questionnaire (secondary outcome).

Primary Hypothesis: Putamen structural node strength (primary outcome) will increase in the training group compared to controls.

Secondary Hypothesis: There will be a significant decrease in emotional problems measured with the Strengths and Difficulties Questionnaire (SDQ) (secondary outcome) in the training group compared to controls.

In our recent published study (Yuan et al., 2019), we demonstrated that diffusion MRI connectome methods can provide reliable and precise network measures, including the node strength, in adolescents.

The SDQ was selected because it is widely used in adolescents to measure internalizing problems and has good psychometric properties (Goodman, 2001).

For more details see section 10.3.3 Metrics.

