9.2. Sample Size and Randomization

The study is powered for medium-large effect size of the meditation training on the putamen node strength. With type I error of 0.05, type II error of 0.2 (power of 80%), two-sided effect size of a Cohen's D of 0.6, the required sample size is N=45 subjects who will be studied before and after the TARA training. Given the length of the study (three months), the required commitment to participation in the training, and based on our experience, we assume an attrition rate of 10%; therefore, the target sample size is 50 subjects per group. Our primary analysis will be a general linear model of putamen node strength at week 12 with terms for baseline node strength, treatment assignment and participant sex. The primary analysis will be intent to treat and will include all randomized participants regardless of treatment receipt or protocol violations.

The only clustering in the trial will be the group delivery of the TARA intervention. We anticipate 4 TARA classes of 10-15 participants. We expect the intraclass correlation to be negligible for the following reasons: a) the TARA instructors are trained in standard procedures, b) we expect formidable individual level variation. We therefore did not include cluster assignment in the sample size calculation. We are going to test this assumption in a sensitivity analysis which extended the primary analysis by inclusion of treatment by TARA class interaction.

To standardize TARA delivery, we have included facilitator training and created a very detailed TARA manual (please see Appendix).

Treatment Assignment Procedures

We will use computer-generated randomization with variable blocks sizes of 4, 6 and 8. Individuals will be randomized with no stratification or restricted except the permuted blocks. We will permute 8 blocks of size 8, 2 blocks of size 6, and 4 blocks of size 4. The treatment assignments will be 1:1 within each block and assignments within a block will be permuted. The only masking will be in the administration of questionnaires and in the interpretation of putamen node strength.

The rationale for the use of randomization is to minimize potential biases.

The study is open label to participants, and thus there is no need for unblinding or unblinding procedures.

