9.4 Interim Analyses and Stopping Rules

This trial will not have any interim analyses. It is itself a preliminary study which will lead to a decision about whether a follow-on study will be conducted in depressed adolescent volunteers.

Safety findings that will trigger a safety review: If 15% of the enrolled study participants experience a Grade 2 (moderate) or Grade 3 (severe) adverse event (AE) related to the TARA study intervention, then a safety review will occur.

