Emotional Problems. Our hypothesis is that training will improve emotional problems as assessed by the SDQ T-score compared with controls. We will use an analysis of covariance (ANCOVA) accounting for sex and fit by maximum likelihood. Stata (College Station, TX) will be used to perform data analyses. We will additionally explore age, pubertal status (as determined by the Tanner stage self-report form (Tanner et al., 1962)), and pre-training associations with the changes through an examination of interaction. Potential pre-/post-training differences in movement during MRI will be accounted for by assessing the number of rejected diffusion directions. Sex as a biological variable: In all analyses described, sex will be included as a factor, we will also test for a randomized arm by sex interaction.

In addition, we will examine relationship between changes in node strength of the putamen and changes in emotion by performing a Spearman rank correlation change in node strength through 12 weeks with change in SDQ through 12 weeks.

Other outcomes.

Adherence. We summarize adherence to training including (i) tabulating the number of participants on the training arm who complete at least 75% of sessions, (ii) calculate the minimum, maximum, median and interquartile range of sessions attended by those randomized to the TARA training arm.

Safety and tolerability of the intervention. Adverse events of grade 2 or higher will be tabulated between the arms and compared by the Fisher exact test. Tolerance scores on the CSRS will be summarized (minimum, maximum, median, interquartile range) at each study visiting on the TARA training arm.

We will tabulate the proportion of participants who are retained through 12 weeks and complete the MRI exam and SDQ questionnaire. These will be compared between the arms by the Fisher exact test.

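### Safety is to be called demonstrated on an observed adverse-event rate below 15%, with no confidence interval planned and no denominator stated

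*Combined protocol and SAP*

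**What the plan says.** Section 9.5.2 lists safety among the other outcomes, after the primary and secondary ones, and gives the decision rule: "The safety of the TARA intervention will be demonstrated if < 15% of the participants experience a grade 2 (moderate") or severe (grade 3) event related to TARA. Section 7.1 gives the same rule: "To demonstrate the safety of the TARA intervention, we will carefully record all adverse events and require that < 15% of the participants experience" such an event.

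The same 15% appears in Section 9.4 as the trigger for a safety review: "If 15% of the enrolled study participants experience a Grade 2 (moderate) or Grade 3 (severe) adverse event (AE") related to TARA.

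The only comparative safety analysis is in Section 9.6: "Adverse events of grade 2 or higher will be tabulated between the arms and compared by the Fisher exact test".

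Section 9.1 gives the allocation: "50 to TARA training and 50 to waitlist control". Section 3 adds that the waitlist arm is to be offered TARA later. The error rates in Section 9.2 belong to the putamen outcome only: "With type I error of 0.05, type II error of 0.2 (power of 80%), two-sided effect size of a Cohen's D of 0.6".

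**The concern.** To say that safety has been demonstrated is to make a claim about the true event rate. The rule supports it with a point estimate alone. No interval, null rate or error rate is attached to the 15%, and no reason is given for choosing it. With about 50 people exposed, the estimate is too imprecise for a figure just under 15% to establish that the true rate is below 15%.

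The denominator is also open. Sections 7.1 and 9.5.2 refer to the participants, and Section 9.4 to the enrolled participants. None of them says whether this means the 50 randomised to TARA, all 100 enrolled, or everyone who eventually receives TARA. The strength of the rule depends heavily on the answer.

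Nothing else in the plan fills the gap. The Fisher test asks whether the arms differ. It does not estimate the TARA rate against 15%, and as worded it counts all events of grade 2 or higher, not only related ones. The Section 9.4 trigger is another observed count.

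At stake is the wording and strength of the safety conclusion in the trial report.

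**Working it through.** **Inputs.** Threshold 15% (Sections 7.1, 9.5.2). Allocation 50 and 50 (Section 9.1). Attrition 10% (Section 9.2) and the 80% retention target (Section 9.5.2), used only to vary the denominator. The true rates below are illustrations and are not in the documents.

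**The plan's own figure.** The safety denominator follows from the sizing for the primary outcome. A two-sample t-test with d = 0.6, two-sided alpha 0.05 and 80% power needs 44.6, so 45 per arm. Then 45/(1 − 0.10) = 50, which agrees with Section 9.2. No precision or error rate is stated for the 15% rule, so there is no figure to reproduce for it.

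**Formulas.** The largest passing count is the largest x with x/n < 0.15. The exact 95% limits are: lower = the 0.025 quantile of Beta(x, n − x + 1); upper = the 0.975 quantile of Beta(x + 1, n − x). The chance of passing at true rate p is P(X ≤ x) for X ~ Binomial(n, p).

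**Denominator = 50 randomised to TARA (assumed).** 7/50 = 14% passes and 8/50 = 16% fails. The exact 95% interval for 7/50 is 5.8% to 26.7%.

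| True rate | P(X ≤ 7), n = 50 |
|---|---|
| 5% | 99.7% |
| 10% | 88% |
| 15% | 52% |
| 20% | 19% |
| 25% | 4.5% |

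**Other readings of the denominator.**

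| Reading | Largest passing count | Exact 95% upper limit | Chance of passing at a true 20% among the exposed |
|---|---|---|---|
| 50 randomised to TARA | 7/50 | 26.7% | 19% |
| 45 remaining after 10% attrition | 6/45 | 26.8% | 18% |
| 40 remaining at 80% retention | 5/40 | 26.8% | 16% |
| 100 exposed, if later waitlist training counts | 14/100 | 22.4% | 8% |
| 100 enrolled, only 50 exposed | 14 events, which is 14/50 = 28% of the exposed | 42.5% (for 14/50; lower limit 16.2%) | 94% |

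The last row assumes that events related to TARA can occur only in the 50 who received it.

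**What an upper-limit criterion would do (n = 50).** Requiring the limit itself to be below 15% allows at most 2/50 (two-sided 95%, upper limit 13.7%) or 3/50 (one-sided 95%, upper limit 14.8%). The chance of passing would be:

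| True rate | At most 2/50 | At most 3/50 |
|---|---|---|
| 2% | 92% | 98% |
| 5% | 54% | 76% |
| 10% | 11% | 25% |
| 15% | 1.4% | 4.6% |

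**The case against.** The strongest reply is that this is a feasibility benchmark in a trial that Section 9.4 itself calls preliminary. Adherence, tolerability and retention are judged on point estimates too, and no test against 15% is claimed. The protocol regards TARA as very low risk, and at a true rate of 5% or 10% the rule passes 99.7% or 88% of the time, as it should. This is a good reason to keep 15% as a benchmark. It does not justify the word demonstrated, which goes further than a benchmark can.

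A reader might infer that the safety declaration decides whether the study in depressed adolescents goes ahead. The documents do not support that. The Go/No-Go criteria in Section 1.1 are an effect size above 0.20 on node strength and at least 80% retention. Section 9.4 says the trial will lead to a decision on a follow-on study, but does not tie that decision to the 15% rule.

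A reader might also infer that participants are protected by this rule alone. They are not. Events are solicited at every TARA session (Section 7.3). Rates are reviewed monthly by the investigators and every six months by the independent monitors, and unexpected related serious events are reviewed as they occur (Section 7.4, Table A). Section 9.4 adds the review trigger. None of these bounds the rate against 15%, but they do provide oversight during the trial.

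Finally, a reader might take 7 of 50, and a pass rate of about one in five at a true 20%, as properties of the plan. They hold only if the denominator is 50, which the plan does not say.

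**Conclusion.** Wrong as written, of minor severity. The rule turns an observed proportion below 15% into a demonstration of safety, with no interval and no stated denominator. If the 50 randomised to TARA are counted, a passing result of 7/50 is compatible with true rates up to 26.7%, and an intervention whose true rate is exactly 15% passes about half the time. Across the possible denominators, the chance that a true 20% rate passes runs from 8% to 94%. These figures assume independent events with a common rate.

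The effect is limited to how the safety result is stated. It does not reach the primary or secondary analyses or the Go/No-Go criteria. A reader might go on to conclude that an upper limit below 15% should be the pass mark. That does not follow. It is a trade-off, because an intervention with a true 5% rate would then fail 46% of the time (100% − 54%) on the two-sided version or 24% (100% − 76%) on the one-sided version.

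**What to change.** In Sections 7.1, 9.5.2 and 9.6:

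- Keep 15% as a descriptive benchmark.
- State that the denominator is the participants randomised to TARA.
- Report the proportion with a related grade 2 or 3 event with its exact (Clopper-Pearson) 95% confidence interval.
- Replace the statement that safety will be demonstrated with a statement that the observed rate is, or is not, below 15%.

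Do not make an upper limit below 15% the required criterion, for the reason given in the verdict. Section 9.4 words its denominator differently, so the passages need to be reconciled on whom they count. This point proposes no change to the review trigger itself.

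The cost is a few lines of text and one interval, with no new data or participants. The downside is a less favourable safety statement: a result of 7/50 would be reported as 14% with an interval reaching 26.7%.

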9.6 Data Analyses

Primary Outcome. To attain the primary objective, we will test the hypothesis that an increase in the node strength of the putamen (dependent variable) will be observed in the training group compared to the controls. This hypothesis will be tested using an analysis of covariance (ANCOVA) accounting for sex and fit by maximum likelihood. Stata (College Station, TX) will be used to perform data analyses. The use of maximum likelihood mitigates susceptibility to missing data. Examination of variable distribution and outlier identification will be performed. We will additionally explore age, pubertal status (as determined by the Tanner stage self-report form (Tanner et al., 1962)), and pre-training associations with the changes through an examination of interaction. Potential pre-/post-training differences in movement during MRI will be accounted for by assessing the number of rejected diffusion directions. Sex as a biological variable: In all analyses described, sex will be included as a factor, we will also test for a randomized arm by sex interaction.

The only clustering in the trial will be the group delivery of the TARA intervention. We anticipate 4 intervention arm clusters of 10-15 participants. We expect the intraclass correlation to be negligible for the following reasons: a) the TARA instructors are trained in standard procedures, b) we expect formidable individual level variation. We are going to test this assumption in a sensitivity analysis which extended the primary analysis by inclusion of treatment by TARA class interaction. We are going to test this assumption in a sensitivity analysis which extended the

primary analysis by inclusion of treatment by TARA class interaction.

To standardize TARA delivery, we have included facilitator training and created a very detailed TARA manual (please see Appendix).

In addition, we will examine relationship between changes in node strength of the putamen and adherence to sessions, proportion of sessions attended, by performing a Spearman rank correlation of TARA adherence (by percentage of sessions attended) and change in node strength. We will use ANCOVA analysis with a treatment by attendance interaction to estimate the putamen node strength which would be achieved with full attendance in all training session.

Secondary Outcome.

Emotional Problems. Our hypothesis is that training will improve emotional problems as assessed by the SDQ T-score compared with controls. We will use an analysis of covariance (ANCOVA) accounting for sex and fit by maximum likelihood. Stata (College Station, TX) will be used to perform data analyses. We will additionally explore age, pubertal status (as determined by the Tanner stage self-report form (Tanner et al., 1962)), and pre-training associations with the changes through an examination of interaction. Potential pre-/post-training differences in movement during MRI will be accounted for by assessing the number of rejected diffusion directions. Sex as a biological variable: In all analyses described, sex will be included as a factor, we will also test for a randomized arm by sex interaction.

In addition, we will examine relationship between changes in node strength of the putamen and changes in emotion by performing a Spearman rank correlation change in node strength through 12 weeks with change in SDQ through 12 weeks.

Other outcomes.

Adherence. We summarize adherence to training including (i) tabulating the number of participants on the training arm who complete at least 75% of sessions, (ii) calculate the minimum, maximum, median and interquartile range of sessions attended by those randomized to the TARA training arm.

Safety and tolerability of the intervention. Adverse events of grade 2 or higher will be tabulated between the arms and compared by the Fisher exact test. Tolerance scores on the CSRS will be summarized (minimum, maximum, median, interquartile range) at each study visiting on the TARA training arm.

We will tabulate the proportion of participants who are retained through 12 weeks and complete the MRI exam and SDQ questionnaire. These will be compared between the arms by the Fisher exact test.

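### Maximum likelihood adds no missing-data protection to a one-follow-up ANCOVA, so the analysis described as covering all randomized participants is a complete-case analysis

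*Combined protocol and SAP*

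**What the plan says.** Section 9.2 defines the primary analysis as "a general linear model of putamen node strength at week 12 with terms for baseline node strength, treatment assignment and participant sex". The same section states: "The primary analysis will be intent to treat and will include all randomized participants regardless of treatment receipt or protocol violations." Section 9.6 describes this analysis as an ANCOVA "accounting for sex and fit by maximum likelihood" and adds: "The use of maximum likelihood mitigates susceptibility to missing data." The maximum-likelihood fit is repeated for the SDQ, the secondary outcome.

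That sentence is the only analytic provision for missing data. No imputation, joint model, auxiliary variable or missing-data assumption is named. The one sensitivity analysis of the primary model concerns TARA class.

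The Schedule of Evaluations (6.1) places the MRI at Visit 1 and Visit 14 only. Section 6.2.2 has baseline completed on the day of randomization, so missing values fall almost entirely on the second scan. Section 9.2 budgets for loss: "we assume an attrition rate of 10%; therefore, the target sample size is 50 subjects per group". The go/no-go criterion (1.1) and the retention target (9.5.2) accept up to 20%.

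**The concern.** Likelihood methods help with missing outcomes when a participant has other modelled responses that carry information about the missing one, as in a repeated-measures model with several visits. Here each participant has one response. If it is missing, the stated model has nothing left with which to inform the treatment effect.

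Followed as written, the plan would therefore report a completers' result as intent to treat and credit it with a protection it does not have. This matters most if participants who attend few TARA sessions also tend to miss the second scan. Attendance is not in the model, so the estimate would move toward the effect in attenders. The plan itself treats attendance as relevant to effect: Section 9.6 correlates it with change in node strength and fits a treatment-by-attendance interaction. The estimate also feeds a go/no-go decision at d > 0.20.

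**Working it through.** **1. The plan's own figure.** Inputs from Section 9.2: two-sided alpha 0.05, power 80%, d = 0.6, 10% attrition. The normal approximation gives 2 × (1.960 + 0.842)² / 0.6² = 43.6, so 44 per arm. The two-sample t-test gives 44.59, so 45 per arm, and 45 / 0.90 = 50. The sample size reproduces and is not in dispute. With the analysed set limited to scanned participants, unadjusted t-test power is 0.844 at 50 per arm, 0.804 at 45 (planned loss) and 0.755 at 40 (the loss the retention target allows).

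**2. What maximum likelihood does here.** Write y0 for baseline and y1 for week-12 node strength. A joint likelihood factors as f(y0 | sex) × f(y1 | y0, arm, sex). The treatment coefficient sits in the second factor. A participant without y1 contributes only the first, and so says nothing about that coefficient. Simulated data with 100 randomized confirm it:

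| Scanned at week 12 | Complete-case least squares | Maximum likelihood |
|---|---|---|
| 71 | 0.31770 | 0.31770 (ML ANCOVA, and two joint models on all 100 rows) |
| 79 | 0.42286 | 0.42286 (joint model) |
| 82 | 0.45955 | 0.45955 (all 100 rows) |

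Maximum likelihood departed from complete-case least squares only when baseline values were missing and a joint model was fitted (8 baselines missing: 0.352 against 0.342). The plan describes no such model.

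**3. When complete-case ANCOVA is sound.** In 3,000 simulations per scenario (assumed baseline-to-follow-up correlation 0.6, true effect 0.60), the mean estimate was 0.600 to 0.603 at 10% and 20% loss, both when loss was completely random and when it depended on baseline. That robustness comes from the covariates, not from maximum likelihood.

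**4. When it is not sound.** The documents give no attendance-specific loss rates, so these are assumptions. In TARA, 20% are low attenders with no effect and 80% have d = 0.6. Of attenders, 5% lack the second scan. A fraction m of low attenders lack it. Control loss is unrelated to outcome.

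- True intent-to-treat effect = 0.8 × 0.6 = 0.48
- TARA loss = 0.8 × 0.05 + 0.2 × m
- Expected complete-case estimate = 0.6 × 0.76 / (0.76 + 0.2 × (1 − m)), where 0.76 = 0.8 × 0.95

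| m | TARA loss | Expected estimate | Bias (SD) |
|---|---|---|---|
| 0.3 | 10% | 0.456 / 0.90 = 0.507 | +0.03 |
| 0.4 | 12% | 0.456 / 0.88 = 0.518 | +0.04 |
| 0.6 | 16% | 0.456 / 0.84 = 0.543 | +0.06 |
| 0.8 | 20% | 0.456 / 0.80 = 0.570 | +0.09 |

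The bias is proportional to the effect in attenders, so it is zero if TARA has no effect in anyone. For scale, the unadjusted standard error at 45 per arm is √(2/45) = 0.21 SD. The bias is about 0.03 / 0.21 = 0.13 of that at planned loss and 0.09 / 0.21 = 0.43 at 20% loss.

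**5. At the go/no-go line.** Under the same assumptions the estimate is inflated by 0.507 / 0.48 = 1.056 at 10% loss and 0.57 / 0.48 = 1.188 at 20%. The expected estimate would exceed 0.20 although the true effect does not for true effects between 0.19 (0.20 / 1.056) and 0.20 at 10% loss, and between 0.17 (0.20 / 1.188) and 0.20 at 20% loss.

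**The case against.** The strongest defence is that the plan works to keep loss small and visible. Sections 6.2.1, 6.2.5 and 8 call for the Visit 14 assessments, MRI included, in participants who leave or stop early. The retention target applies regardless of adherence. Section 9.6 compares MRI and SDQ completion between arms by Fisher's exact test. If these provisions work, high scan loss among low attenders will not occur. This stands as a limit on the size of the problem, but it does not rescue the sentence. Collection reduces loss and the comparison can reveal it; neither corrects the estimate for what remains. The plan still budgets for 10% attrition and, under Section 4.2, takes no second scan after a new pregnancy.

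It is also fair to say that complete-case ANCOVA may be valid, as step 3 shows. The plan does not state the assumption that would make it so.

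Three stronger readings should be resisted.

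- A reader might infer that the primary result must be biased, or that a false positive is likely. The documents do not support this: the bias needs both attendance-related scan loss and an attendance-related effect, and under that mechanism it vanishes when TARA does nothing.
- A simulation in which TARA participants with low node-strength response drop out gives larger numbers: a true 0.60 estimated as 0.72 at 10% loss and 0.80 at 20%, and a true zero as 0.11 and 0.21. Table 1 in Section 6.2.3 keeps participants blinded to the mechanistic outcome, so loss driven directly by it is hard to motivate.
- A reader might take the maximum-likelihood wording to mean a z reference and a residual variance divided by n, with slight type I error inflation. The plan specifies neither, and a general linear model or ANCOVA is ordinarily tested with t or F.

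**Conclusion.** The point holds in this form: the missing-data sentence is wrong for the stated model, and the promise to include all randomized participants cannot be met by that model when second scans are missing. That conclusion is algebraic and needs no assumption beyond one follow-up value per participant and complete baselines. The same applies to the SDQ ANCOVA, which also has one follow-up.

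The consequence for the estimate is conditional. There is no bias if loss depends only on baseline, arm and sex and the model is right. Under the assumed attendance mechanism the bias is +0.03 SD at the planned rate of loss and +0.09 SD at 20% TARA loss. This is modest against d = 0.6 and below one standard error, and it would tip the expected go/no-go result only for true effects just under 0.20. The figures illustrate a range and are not predictions. The sample size and the design are unaffected. The change should be made because the plan states a safeguard that is absent and a better method needs no new data.

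**What to change.** Delete the sentence on maximum likelihood and missing data. For the primary analysis, multiply impute missing week-12 node strength separately by arm from baseline node strength, sex, age, the Visit 14 SDQ and, in TARA, the number of sessions attended. The ANCOVA then covers all randomized participants. Attendance is already recorded (5.4), and the Visit 14 SDQ is electronic (6.2.5), so it can be obtained without a scan. Report complete-case ANCOVA alongside and state its missing-at-random assumption. Add a delta-adjusted sensitivity analysis that shifts imputed TARA values downward. Align the SDQ paragraph in Section 9.6.

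The cost is SAP wording and some Stata code. In a simulation of the mechanism assumed above, imputation cut the bias from +0.03 to +0.01 SD at 10% TARA loss and from +0.09 to +0.04 SD at 20%, while the standard error rose by about 1% to 17%. Some bias remains when loss is heavy because few low attenders are left to inform the imputation. With 50 in TARA, 10 low attenders and m = 0.8, only 2 of the 10 would be scanned. That is why the delta-adjusted analysis is needed as well. At the very least, the plan should drop the sentence, name the complete-case set as the one analysed, and state the assumption under which it is valid.
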